10 STATISTICAL ANALYSIS

All statistical analysis will be performed under the direction of Hutchison MediPharma personnel. Any data analysis carried out independently by the investigator should be submitted to Hutchison MediPharma prior to publication or presentation.

The final analysis will be based on patient data collected through study discontinuation or study termination. There is no planned formal interim analysis. However, the accrued data may be analyzed for internal decision-making purposes, for example to provide information for a potential Phase 3 study design.

Final analysis for each cohort will occur once the last patient had been followed for sufficient time for the analysis of primary endpoint. For instance, for Arm A, final analysis will occur when the last patient had been on treatment for at least 16 weeks or discontinued early following discontinuation criteria. Timing of final analyses for cohorts may be combined if they occur close together. Details of the statistical analysis and data reporting will be provided in the Statistical Analysis Plan (SAP) document finalized prior to database lock.

Data will be summarized using descriptive statistics (continuous data) and/or contingency tables (categorical data) for demographic and baseline characteristics, efficacy measurements, safety measurements, and PK measurements. Information regarding compliance with efficacy testing and availability of data will be documented. Graphical techniques (eg, waterfall plots, Kaplan-Meier curves) will be used when such methods are appropriate and informative. The baseline value used in each analysis will be the last (most recent) pre-treatment value. Time to event variables will be summarized descriptively using Kaplan-Meier medians and quartiles. Analyses will be based upon the observed data unless methods for handling missing data are specified. Analyses will be performed using SAS® (Version 9.1 or higher).

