10.1 Determination of Sample Size

The total number of patients enrolled will depend on the number of dose escalations and the need to further characterize individual cohorts in the expansion phase.

The planned enrollment for this study is approximately 95 to 150 patients, including 35 patients in the dose escalation phase, and approximately 115 patients for the dose expansion phase. Dose expansion phase will enroll patients in specific disease cohorts, 30 patients in the BTC Arm, at least 15 patients each in the pNET and epNET arms, and 55 patients in the STS arm (10 patients with LMS, 10 patients with UPS, 10 patients with epithelioid sarcoma, 10 patients with angiosarcoma, 10 patients with SS, and 5 patients with PVNS).

Sample size for Arm A: BTC cohort in dose expansion phase:

The PFS rate at 16 weeks was selected as the primary endpoint for the expansion phase of the study in patients with BTC. The PFS rate at 16 weeks is defined as the percent of patients without evidence of disease progression or death after 16 weeks on study among the PFS-evaluable patients.

For a BTC cohort with at least 30 evaluable patients, the treatment effect may be considered positive if there are at least 9 evaluable patients without evidence of progression or death after 16 weeks on study. This event will occur with probabilities 90.6% (true positive

rate) if the true PFS rate at 16 weeks is 40%, and 2.8% (false positive rate) if the true PFS rate at 16 weeks is 15%.

In addition, for a cohort with 30 evaluable patients, if 9 (30.0%) patients, or 10 (33.3%) patients without progression or death at 16 weeks are observed, then the lower limit of the 80% two-sided CIs for PFS rate at 16 weeks would be 19.0% and 21.8%, respectively.

Sample size for Arm B: pNET cohort in dose expansion phase:

For a pNET cohort with at least 15 evaluable patients, the treatment effect may be considered positive if there are at least 6 evaluable patients without evidence of disease progression or death after 11 months on study. This event will occur with probabilities 84.9% (true positive rate) if the true PFS rate at 11 months is 50%, and 4.9% (false positive rate) if the true PFS rate at 11 months is 19%.

In addition, for a cohort with 15 evaluable patients, if the 6 (40%) patients or 7 (47%) patients without progression or death at 11 months are observed, the lower limit of the 80% two-sided CIs for PFS rate at 11 months would be 22.6% and 28.2%, respectively.

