Sample size for Arm C: epNET cohort in dose expansion phase:

For a pNET cohort with at least 15 evaluable patients, the treatment effect may be considered positive if there are at least 6 evaluable patients without evidence of disease progression or death after 11 months on study. This event will occur with probabilities 84.9% (true positive rate) if the true PFS rate at 11 months is 50%, and 4.9% (false positive rate) if the true PFS rate at 11 months is 19%.

In addition, for a cohort with 15 evaluable patients, if the 6 (40%) patients or 7 (47%) patients without progression or death at 11 months are observed, the lower limit of the 80% two-sided CIs for PFS rate at 11 months would be 22.6% and 28.2%, respectively.

Sample size for Arm D: STS cohort in dose expansion phase:

Arm D will consist of 6 cohorts of STS subtypes. The LMS, UPS, epitheloid sarcoma, angiosarcoma, and SS cohorts will enroll at least 10 evaluable patients each. The treatment effect may be considered positive if there are at least 3 evaluable patients in each cohort without evidence of disease progression or death after 4 months on study. This event will occur with probabilities of 83.3% (true positive rate) if the true PFS rate at 4 months is 40%, and 7% (false positive rate) if the true PFS rate at 4 months is 10%.

For the PVNS cohort, it is planned to enroll 5 evaluable patients. This sample size is based on feasibility.

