6.2. SAFETY ANALYSIS SET (SAS) – (ALL TREATED POPULATION)

This analysis set includes all patients who have received at least one dose of surufatinib. Safety data will be evaluated based on this analysis set outcome. Patients in the SAS will be analyzed by their actual dose initially received. If patients have dose reduction during the study, all data will be summarized/ analyzed based on the initial dose of study medication received.

All safety analyses except for DLT summaries will be based on the SAS. Efficacy endpoints PFS and OS (OS applies to BTC and STS cohorts only) will be analyzed based on this analysis set.

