16. EFFICACY OUTCOMES

Efficacy data will be summarized by dose cohort in dose escalation phase and by disease cohort in dose expansion phase. PFS and OS will be analyzed for the SAS. The other efficacy variables (BOR, ORR, DCR, TTR, and DOR) will be analyzed for EAS.

Treatment efficacy will be evaluated by using tumor responses which will be assessed and documented at Screening, Day 1 of Cycle 2 and every 8 (+/-1 week) weeks on Day 1 of every other cycles afterwards (i.e. Cycle 4, 6... etc), until the occurrence of progressive disease (PD) according to the standard of Response Evaluation Criteria in Solid Tumors (RECIST) Version 1.1. Confirmation of CR and PR is required at no less than 4-week intervals between the date of initial response/progression and the confirmation assessment date. When the patient interrupts study medication due to AEs or other reasons, the evaluation should be conducted as scheduled. For suspected cases of PD before the start of the next scheduled assessment, additional tumor assessments will be done.

Tumor responses data are captured on CRF page "Tumor Measurement - Target Lesions", "Tumor Assessment - Non-Target lesions", "Tumor Assessment - New Lesions" and "Assessment of Disease". The confirmed best overall response (BOR, refer Section 16.1.2) will be summarized for EAS and will be presented together with summaries for objective response rate (ORR) and disease control rate (DCR).

The baseline sum of diameters will be presented with other baseline characteristics.

Tumor assessments for target lesion, non-target lesion, and new lesion will be presented in a listing. In addition, a listing of overall response including lesion responses, sum of diameters, and the corresponding change from baseline in tumor diameter will be provided.

Tumor assessment performed at the treatment completion visit (details can be found in SAP Section 7.3) is an eligible data point for the derivation of all efficacy endpoints, following the derivation rules described in Section 16.1.

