16.1. EFFICACY VARIABLE(S) & DERIVATION(S)

16.1.1. Progression-Free Survival

Progression-free survival (PFS) is defined as the time (in months) from the start date of study medication (Day 1) until the date of objective disease progression as defined by RECIST Version 1.1 or death (by any cause in the absence of progression), whichever occurred earlier.

The PFS time will always be derived based on scan/assessment dates and not based on visit dates. RECIST

CCI

assessments/scans contributing towards a particular visit, which consists of assessment for “Non-Target lesions”, “Target lesions”, and “New lesions”, may be performed on different dates. The following rules will be applied:

- Date of progression will be determined based on the earliest of the dates of the radiological component that triggered the progression.
- When censoring a patient for PFS the patient will be censored at the latest of the dates contributing to a particular overall visit assessment.

If a patient has not experienced progressive disease (PD) or died before the end of study for any reason, progression-free survival will be censored at the date of the last evaluable tumor assessment on or prior to the PD, which is not necessarily confirmed.

Three additional rules apply to PFS only:

[figure not shown]
- If a patient misses two or more consecutive tumor assessment visits, and showed PD or death afterwards, PFS will be censored at the date of last tumor assessment prior to the consecutive missed visits. Two consecutive missed/non-evaluable tumor assessment visit window is calculated as $2*(8 \text{ weeks}+1\text{week window time})$, which is 126 days.
- If a patient reports no baseline tumor assessments or has no evaluable tumor assessment visits after the first dose of study medication, PFS will be censored at the start date of study medication unless they die within two consecutive tumor assessments since the first dose of study medication, i.e., PFS=1 day.
- Of note that tumor assessments after the first new anti-cancer treatment (same day inclusive) will be considered inadequate. If a patient starts new anti-tumor therapy initiated prior to documented disease progression or death on study, PFS will be censored at the date of the last tumor assessment prior to or on the date of new anti-tumor therapy.

See Table 1 for the detailed information of event/censoring rules for PFS:

Table 1: PFS Events/censoring rules

Description	Event/Censor	Date of Event/Censor

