Documented progression before start use of new anti-tumor therapy and no two consecutive missed tumor assessment visits	Event	Date of documented disease progression
Death without progression and without use of new anti-tumor therapy and without missing two consecutive tumor assessment visits	Event	Date of death
Death or progression after two or more consecutive missed tumor assessments	Censor	Date of last evaluable tumor assessment prior to the consecutive missed tumor

CCI

		assessment visits
No evaluable baseline or post-baseline tumor assessment and no new lesion found and no death within two scheduled tumor assessment visits post-baseline	Censor	Date of first dosing of study medication
New anti-tumor therapy started prior to documented disease progression or death on study	Censor	Date of last evaluable tumor assessment before start use of new anti-tumor therapy
No progression and no death before end of study or data cut-off	Censor	Date of last evaluable tumor assessment

Note: Symptomatic deterioration will not be regarded as a progression event.

The PFS will be programmatically derived as follows:

1. If a patient had disease progression or death, then

$PFS \text{ (month)} = ([\text{date of earliest evidence of disease progression or death (including death from any cause)} - \text{start date of study medication}] + 1) / 30.4375$; Otherwise,

2. If the patient was known to have developed one of above censoring criteria, then the PFS is censored and

$PFS \text{ (month)} = ([\text{date of censoring} - \text{start date of study medication}] + 1) / 30.4375$.

3. Special scenario such as two or more consecutive missing tumor assessment visits or new anti-cancer treatment will be handled according to the rules provided in Table 1.

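### Arm A can be analysed before the scan that settles 16-week status, which censors clean late enrollees before the landmark, and the go count has an undefined denominator

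*SAP*

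**What the plan says.** Scans take place at screening, then at "Day 1 of Cycle 2 and every 8 (+/-1 week) weeks on Day 1 of every other cycles afterwards (i.e. Cycle 4, 6... etc" (SAP section 16; Protocol 5.1.2 gives the same interval). SAP 16.1.1 states: "The PFS time will always be derived based on scan/assessment dates and not based on visit dates". Deaths are dated at death. Table 1 of that section covers patients with "No progression and no death before end of study or data cut-off" and censors them at the last evaluable tumour assessment. Scans for suspected progression and scans at treatment completion also count (SAP section 16).

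The primary landmarks are 16 weeks (Arm A), 11 months (Arms B and C) and 4 months (Arm D). SAP 16.2 reports Kaplan-Meier probabilities at these times.

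Protocol 10.1 adds a go count for each arm. For Arm A the rate is "the percent of patients without evidence of disease progression or death after 16 weeks on study among the PFS-evaluable patients", and at least 9 such patients out of 30 may be considered positive. Neither Protocol 10.2 nor SAP section 6 defines a PFS-evaluable set. Of the Safety Analysis Set (SAS), SAP 6.2 says: "Efficacy endpoints PFS and OS (OS applies to BTC and STS cohorts only) will be analyzed based on this analysis set".

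On timing, Protocol section 10 says that for Arm A "final analysis will occur when the last patient had been on treatment for at least 16 weeks", or has discontinued early.

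**The concern.** A landmark that no scheduled scan covers is read from the scan before it. That is tolerable if every patient also has imaging after the landmark, because a clean later scan confirms that no event was dated by then. The Arm A trigger removes that safeguard for the last patients enrolled. Those with an event dated after day 85 stay in the analysis as events; those still clean leave it at day 85. Censoring then depends on outcome and pulls the estimate down.

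The go count inherits the gap. It does not say whether a treated patient censored before the landmark is a success, a failure or outside the denominator. It is the only stated basis for calling an arm positive, and in Arm A the threshold is only 9 patients.

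**Working it through.** **1. Printed figures.** Exact binomial tails, true positive / false positive:
- Arm A, at least 9 of 30, rates 40% / 15%: 0.9060 / 0.0278.
- Arms B and C, at least 6 of 15, 50% / 19%: 0.8491 / 0.0490.
- Arm D, at least 3 of 10 per subtype, 40% / 10%: 0.8327 / 0.0702.

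All match Protocol 10.1, including "2.8% (false positive rate) if the true PFS rate at 16 weeks is 15"% and "7% (false positive rate) if the true PFS rate at 4 months is 10"%.

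**2. Landmarks against windows.** First dose is day 1 and a month is 30.4375 days (SAP 7.7).
- Arm A: 16 × 7 = day 112. Arm D: 4 × 30.4375 = day 121.75. Both lie between the windows for day 85 (78–92) and day 141 (134–148).
- Arms B and C: 11 × 30.4375 = day 334.8, between the windows for day 309 (302–316) and day 365 (358–372).

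**3. Effect of the Arm A trigger.** Neither document gives a PFS curve, an accrual period or the share of between-scan events that get dated, so these are assumptions: exponential PFS, even accrual over L days, scans on nominal days, and a fraction f of events in days 85–112 dated in that gap by death or an extra scan.

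- Share of patients with 112 to 141 days of follow-up at the cut-off: w = (141 − 112)/L = 29/L. For 3, 6 and 12 months, w = 0.318, 0.159 and 0.079.
- Clean at day 85: S85 = p^(85/112), which is 0.4989 for p = 0.40 and 0.2370 for p = 0.15.
- Conditional probability of a dated event in days 85–112: q = f(S85 − p)/S85.
- Full-follow-up rate: S85(1 − q).
- Undetermined patients: 30 · w · S85(1 − q).
- After day 85 the late patients stay at risk only if they have a dated event, so Kaplan-Meier at day 112 = S85 · (1 − w)(1 − q)/[(1 − w) + wq].

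Example, p = 0.40, 3 months, f = 0.5: q = 0.0991; full-follow-up rate 0.4494; Kaplan-Meier = 0.4989 × (0.6824 × 0.9009)/(0.6824 + 0.0315) = 0.4296; shortfall 2.0 points.

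| p | Accrual | Undetermined of 30 (f = 0 / 0.5 / 1) | Shortfall in points (f = 0 / 0.5 / 1) |
|---|---|---|---|
| 0.40 | 3 months | 4.8 / 4.3 / 3.8 | 0 / 2.0 / 3.4 |
| 0.40 | 6 months | 2.4 / 2.1 / 1.9 | 0 / 0.8 / 1.4 |
| 0.40 | 12 months | 1.2 / 1.1 / 1.0 | 0 / 0.4 / 0.7 |
| 0.15 | 3 months | 2.3 / 1.8 / 1.4 | 0 / 1.5 / 2.2 |
| 0.15 | 6 months | 1.1 / 0.9 / 0.7 | 0 / 0.6 / 1.0 |
| 0.15 | 12 months | 0.6 / 0.5 / 0.4 | 0 / 0.3 / 0.5 |

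So roughly 0.5 to 5 patients are undetermined and the shortfall is about 0 to 2.5 points, except for 3-month accrual at p = 0.40 with most gap events dated.

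Scatter of scans within the window works in the same direction, because clean late patients leave before others are scanned. Take the widest case, scans spread evenly over the window, p = 0.40, f = 0. With c = 0.40^(56/112) = 0.6325 and a = (1 − w)c, Kaplan-Meier = 0.40^(29/112) × a^[(1 − c)/(1 − a)]. This is 0.7888 × 0.5808 = 0.458 for 3 months and 0.7888 × 0.6214 = 0.490 for 12 months, against 0.499: 4.1 and 0.9 points low.

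**4. The count.** At a 40% rate, 30 × 0.40 = 12 successes are expected. With f = 1, undetermined patients leave 12 − 3.8 = 8.2 confirmed for 3-month accrual and 12 − 1.0 = 11.0 for 12-month accrual, against a threshold of 9. The denominator matters too: applying 9 to an illustrative 33 treated patients gives a false-positive rate of 4.9%.

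**5. Later cut-off.** If the last patient is followed to day 148, every patient still on schedule has a scan after day 112. The undetermined group and the shortfall from this source then vanish.

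**The case against.** The trigger says at least 16 weeks and is offered as an example of sufficient follow-up. SAP 5.4 places the final analysis after database lock, so the actual cut-off may be later. Only the last patients enrolled are affected. Landmarks between 8-weekly scans are ordinary, the go rule is worded as guidance, and both documents disclaim formal testing (Protocol 10.3, SAP 7.6). All of this is fair and limits the size. None of it rules out the early cut-off, which the text expressly allows.

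A reader might go further and infer that the printed operating characteristics are wrong. If 15% and 10% were true rates at the nominal times and only scheduled scans dated events, the false-positive rates would be 26.7% (Arm A) and 32.3% (Arm D subtype). The documents do not support this. Both define PFS by documented events, and neither describes an underlying curve observed continuously. Zero dating between scans also contradicts the provision for extra scans.

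A reader might also infer that using the scan before or after the landmark could reverse the go decision. That too lacks support: progression first seen at day 141 is dated day 141, so the patient was progression-free at 16 weeks.

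**Conclusion.** The point holds as a timing defect in Arm A with a loosely specified go count. The expected effect is roughly 0.5 to 5 of 30 patients undetermined and a 16-week rate about 0 to 2.5 points too low. The nominal-day extreme is 3.4 points, and wide scatter within scan windows could add to it. The error is conservative: it works against the drug. These sizes rest on exponential PFS and on assumed accrual and dating of gap events; the direction does not.

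The go counts and printed binomials stand, provided that the planning rates are on the scan-dated scale, which the plan should say. For Arms B, C and D the protocol gives only the general principle of sufficient follow-up, so the same gap is possible there but not written in. The Appendix 1 flowchart was not in the supplied text; the schedule here comes from the protocol body and SAP section 16.

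**What to change.** 1. In Protocol section 10, set each arm's data cut-off after the last patient's first scheduled scan window past the landmark has closed: day 148 for Arms A and D, day 372 for Arms B and C.
2. In Protocol 10.1 and SAP 16.2, state that the go count uses the scan-dated PFS of SAP 16.1.1, with failure meaning an event dated on or before the landmark, and that the null and alternative rates are on that scale.
3. Take the count in the SAS in place of the undefined PFS-evaluable set. List treated patients censored before the landmark and do not count them as successes. Do not require a later scan for evaluability: that would drop clean patients while keeping early failures.

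Keep the scan schedule, go counts and printed binomials. Efficacy was already summarised for BTC, pNET and epNET in 2019 and for pNET and epNET in 2020 (SAP 5.2, 5.3), so the wording should follow the existing PFS rule and not set a new criterion.

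Cost: wording changes and a later cut-off for the last patient, by 148 − 112 = 36 days (A), 148 − 122 = 26 days (D) and 372 − 335 = 37 days (B and C), about 4 to 5 weeks. No extra scans or patients are needed.

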16.1. EFFICACY VARIABLE(S) & DERIVATION(S)

16.1.1. Progression-Free Survival

Progression-free survival (PFS) is defined as the time (in months) from the start date of study medication (Day 1) until the date of objective disease progression as defined by RECIST Version 1.1 or death (by any cause in the absence of progression), whichever occurred earlier.

The PFS time will always be derived based on scan/assessment dates and not based on visit dates. RECIST

CCI

assessments/scans contributing towards a particular visit, which consists of assessment for “Non-Target lesions”, “Target lesions”, and “New lesions”, may be performed on different dates. The following rules will be applied:

- Date of progression will be determined based on the earliest of the dates of the radiological component that triggered the progression.
- When censoring a patient for PFS the patient will be censored at the latest of the dates contributing to a particular overall visit assessment.

If a patient has not experienced progressive disease (PD) or died before the end of study for any reason, progression-free survival will be censored at the date of the last evaluable tumor assessment on or prior to the PD, which is not necessarily confirmed.

Three additional rules apply to PFS only:

[figure not shown]
- If a patient misses two or more consecutive tumor assessment visits, and showed PD or death afterwards, PFS will be censored at the date of last tumor assessment prior to the consecutive missed visits. Two consecutive missed/non-evaluable tumor assessment visit window is calculated as $2*(8 \text{ weeks}+1\text{week window time})$, which is 126 days.
- If a patient reports no baseline tumor assessments or has no evaluable tumor assessment visits after the first dose of study medication, PFS will be censored at the start date of study medication unless they die within two consecutive tumor assessments since the first dose of study medication, i.e., PFS=1 day.
- Of note that tumor assessments after the first new anti-cancer treatment (same day inclusive) will be considered inadequate. If a patient starts new anti-tumor therapy initiated prior to documented disease progression or death on study, PFS will be censored at the date of the last tumor assessment prior to or on the date of new anti-tumor therapy.

See Table 1 for the detailed information of event/censoring rules for PFS:

Table 1: PFS Events/censoring rules

Description	Event/Censor	Date of Event/Censor
Documented progression before start use of new anti-tumor therapy and no two consecutive missed tumor assessment visits	Event	Date of documented disease progression
Death without progression and without use of new anti-tumor therapy and without missing two consecutive tumor assessment visits	Event	Date of death
Death or progression after two or more consecutive missed tumor assessments	Censor	Date of last evaluable tumor assessment prior to the consecutive missed tumor

CCI

		assessment visits
No evaluable baseline or post-baseline tumor assessment and no new lesion found and no death within two scheduled tumor assessment visits post-baseline	Censor	Date of first dosing of study medication
New anti-tumor therapy started prior to documented disease progression or death on study	Censor	Date of last evaluable tumor assessment before start use of new anti-tumor therapy
No progression and no death before end of study or data cut-off	Censor	Date of last evaluable tumor assessment

Note: Symptomatic deterioration will not be regarded as a progression event.

The PFS will be programmatically derived as follows:

1. If a patient had disease progression or death, then

$PFS \text{ (month)} = ([\text{date of earliest evidence of disease progression or death (including death from any cause)} - \text{start date of study medication}] + 1) / 30.4375$; Otherwise,

2. If the patient was known to have developed one of above censoring criteria, then the PFS is censored and

$PFS \text{ (month)} = ([\text{date of censoring} - \text{start date of study medication}] + 1) / 30.4375$.

3. Special scenario such as two or more consecutive missing tumor assessment visits or new anti-cancer treatment will be handled according to the rules provided in Table 1.

